### 2.3 Exploratory Objectives

2.3.1 Compare the proportion of WOC vs non-WOC EAQ201 participants with COVID-related employment change, a composite measure.

2.3.2 Compare the proportions of WOC vs non-WOC EAQ201 participants with COVID-specific perceived distress and perceived susceptibility to COVID and breast cancer.

2.3.3 Compare the proportions of WOC vs non-WOC EAQ201 participants with relative increase in smoking and alcohol use, risk factors for breast cancer.

2.3.4 Compare participant-reported quality of life, anxiety and depression between WOC and non-WOC EAQ201 participants.

2.3.5 Assess the effects of sociodemographic characteristics, and federal-, state- or local-level COVID-19 factors on TMIST participation, in WOC vs non-WOC.

Rev. Add2 **3. Selection of Sites**

All interested NCORP and the three selected non-NCORP TMIST sites located in the United States will be invited to participate. There will be no specific exclusion criteria (i.e., minimum number of cases) because we would like to include a wide variety of different systems to better understand the variability in available financial resources and participant experiences.

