**3.1 Eligibility Criteria for Participants**

Rev. Add2

- \_\_\_\_\_ 3.1.1 Participant must have been eligible for and declined EA1151/TMIST in the preceding 6 months.
- \_\_\_\_\_ 3.1.2 Participant must be able to complete questionnaires in English.
- \_\_\_\_\_ 3.1.3 Participant must have a U.S. zip code.

---

Physician Signature

Date

**OPTIONAL:** This signature line is provided for use by institutions wishing to use the eligibility checklist as source documentation.

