EAQ201 project manager will create a list of eligible sites based on EA1151 recruitment and enrollment status and will notify CTSU of ECOG-ACRIN clearance of this site qualification criteria. Site submission of required IRB documentation to NCI CIRB will be monitored in RSS weekly by the EAQ201 project manager who will report site activation clearances in CTSU weekly to the EAQ201 study chair by [define weekly communication mechanism you prefer here]. All sites that plan to open EAQ201 are strongly encouraged to activate EAQ201 within 30 days of ECOG-ACRIN activation of the trial as there will be no maximum number of subjects that can be enrolled in the trial at any one site and enrollment is expected to be completed within a few months.

EAQ201 project manager will reach out weekly to all eligible EA1151 sites to remind them about the EAQ201 study and obtain IRB approval through NCI CIRB. This outreach will occur by email to TMIST PI and TMIST lead coordinator until the site opens EAQ201, declines to participate, or EAQ201 enrollment reaches 50% of planned enrollment, 500.

**Participant Recruitment Plan:** All participating EAQ201 TMIST sites will be expected to approach at least 20 women per month in person or over the phone as part of their TMIST recruitment effort while EAQ201 is open to participant enrollment with at least 5 women approached that are classified as Women of Color [definition] according to information documented in the site's electronic medical record system.

All women presenting for screening mammography who meet the eligibility criteria for EA1151 but ultimately decline to participate in EA1151 should be immediately invited to participate in EAQ201 by EA1151 site designated recruiters.

All EAQ201 TMIST sites are expected to keep local TMIST recruitment logs for duration of EAQ201 enrollment period. The first two weeks of local TMIST recruitment logs for each site are to be submitted to the EAQ201 project manager to confirm that recruitment effort is happening for TMIST and to monitor number of WOC TMIST declines at the site. This information will be summarized across all sites for reporting to the EAQ201 central trial team to compare to EAQ201 enrollment rates at each site to determine if site is on track to complete within timeline planned and that overall WOC versus non-WOC participation ratio is within 10%-25% range planned.

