### 7.3 Secondary Objectives

Two-sample proportion tests (e.g., Z-test based on normal approximations or Fisher's exact test) will be used to compare the proportions of WOC vs non-WOC EAQ201 participants with 1) COVID-related change in their material condition; 2) COVID-specific perceived financial distress. Logistic regressions may be performed to adjust for potential confounders during the comparisons. Missing data will be managed as below (See [7.5](#)).

The proportion of WOC in EAQ201 participants will be compared to the proportion of WOC in TMIST participants using the one-sample proportion test. Based on the TMIST data, the proportion of WOC in TMIST participants is around 25%. Then we will have 80% power to detect a difference of 3.9% using a two-sided exact test with a significant level of 0.05.

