### 7.4 Assess the effects of sociodemographic characteristics, and federal-, state- or local-level COVID-19 factors on TMIST participation, in WOC vs non-WOC.

For the exploratory objective ([7.1.3.5](#)), we will compare the effects of sociodemographic characteristics, federal-, state- or local-level factors (e.g. maximum number of COVID-19 cases, state unemployment during shelter-in-place, local unemployment during shelter-in-place) on TMIST participation, stratified by WOC vs non-WOC. We will fit a logistic regression model with TMIST participation status (EAQ201 participant or TMIST participant) as the response variable to investigate other sociodemographic (e.g., marital status, neighborhood SES, insurance type), federal-, state- or local-level factors (see **Table 2**). Regression modeling will be conducted with and without stratification by WOC vs non-WOC.

The analysis set will include the 1000 EAQ201 participants from this study and a corresponding number of TMIST participants, who will be randomly selected from the enrolled participants in the main TMIST study. The selection will be stratified by site and enrollment time. Assuming that the proportion of overall EAQ201 participants is from 0.20 to 0.50, **Table 5** below shows the power analysis of testing for the odds ratio in the logistic regression. The variables of interest can be continuous or categorical (binary). For instance, 2000 women (1000 EAQ201 participants versus 1000 randomly selected TMIST participants) achieves 90% power at a 0.050 significance level to detect a change in the proportion of EAQ201 participants from 0.50 at the mean of the testing variable to 0.538 when the value of the variable is increased to one standard deviation above the mean. This change corresponds to an odds ratio of 1.165. An adjustment was made since a multiple regression of the independent variable of interest on other independent variables in the logistic regression obtained an R-Squared of 0.10.

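### Section 7.3 tests the WOC share of EAQ201 decliners against one TMIST percentage without restricting to EAQ201 sites or adjusting for site, so site mix alone can produce a rejection in either direction.

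*Combined protocol and SAP*

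**What the plan says.** Objective 2.2.3 asks whether WOC make up a different share of TMIST decliners, as represented by EAQ201 participants, than of women who joined TMIST. Section 7.1.2.3 predicts a higher share among decliners. Section 7.3 says that the EAQ201 share "will be compared to the proportion of WOC in TMIST participants using the one-sample proportion test", gives the reference value ("Based on the TMIST data, the proportion of WOC in TMIST participants is around 25" per cent), and adds: "Then we will have 80% power to detect a difference of 3.9% using a two-sided exact test with a significant level of 0.05". It names no site restriction, stratification or adjustment for this comparison. The optional logistic adjustment in 7.3 belongs to the two WOC versus non-WOC endpoint comparisons that precede it.

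On where EAQ201 women come from, Section 3 says "All interested NCORP and the three selected non-NCORP TMIST sites located in the United States will be invited to participate". Section 5 says "there will be no maximum number of subjects that can be enrolled in the trial at any one site".

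Alignment with TMIST women appears in two other places. Section 5 limits the sociodemographic comparison to women who joined TMIST in the same period; Table 1 counts race/ethnicity among the sociodemographics. Section 7.4 draws TMIST comparators for the exploratory participation model, and there "The selection will be stratified by site and enrollment time". Neither provision is carried into 7.3.

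Eligibility criterion 3.1.2 reads "Participant must be able to complete questionnaires in English".

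**The concern.** The question in 2.2.3 is about behavior: given the same invitation, are WOC more likely to decline? A comparison of two pooled percentages answers it only if both groups come from the same sites in the same proportions. Here they need not. Sites choose whether to open EAQ201, and a few fast-accruing sites could supply much of the sample. Section 5 also expects EAQ201 sites to approach at least 5 WOC among at least 20 women a month. The documents state no such floor for TMIST sites that do not open EAQ201.

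If EAQ201 accrual leans toward sites with many WOC, the test can falsely support the hypothesis. If it leans the other way, the test can show the opposite or hide a real difference. Objective 2.2.3 calls this a key hypothesis, yet it has less control for site than the exploratory model in 7.4.

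The plan's own figures show the difficulty. Section 7.2 cites 16% WOC among TMIST decliners (DCP-001) and 7.3 cites about 25% among participants, a 9-point gap opposite to the hypothesis. Section 7.2 extrapolates from DCP-001 to non-NCORP sites, which suggests that DCP-001 covers NCORP sites. Different site bases may therefore contribute to the gap. The analysis in 7.3 could not separate that from a real difference in participation.

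**Working it through.** **Inputs.** Reference share 0.25, two-sided exact test, alpha 0.05, 80% power, 3.9-point difference (Section 7.3). N is not restated in 7.3; 1000 is taken from 7.2 and 7.4 ("The analysis set will include the 1000 EAQ201 participants from this study").

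**1. The plan's figure.** For X ~ Binomial(1000, 0.25), the equal-tailed exact test rejects if X ≤ 222 or X ≥ 278. The tail probabilities are 0.0213 and 0.0232, so the actual alpha is 0.0445.
- Power at 21.1%: 81.4%.
- Power at 28.9%: 78.8%.

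The stated 80% is reproduced to within 2 points.

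**2. Site mix with no within-site difference.** Suppose that at every site decliners and participants have the same WOC share, but the EAQ201 site weights move the pooled share to 0.25 + b or 0.25 − b. The rejection probability is P(X ≤ 222) + P(X ≥ 278) at that share:

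| Shift b | EAQ201 share higher | EAQ201 share lower |
|---|---|---|
| 1 point | 10.7% | 10.0% |
| 2 points | 29.6% | 28.8% |
| 3 points | 56.8% | 57.8% |
| 3.9 points | 78.8% | 81.4% |
| 5 points | 94.1% | 96.1% |

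The middle column is the rate at which the test rejects when site mix alone raises the EAQ201 share. Nearly all of those rejections fall in the direction of the hypothesis.

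**3. How much site mix this takes (assumed values).** Take two groups of sites with 10% and 40% WOC that contribute equally to TMIST: 0.5 × 0.10 + 0.5 × 0.40 = 0.25.
- EAQ201 weights 37/63: 0.37 × 0.10 + 0.63 × 0.40 = 0.289.
- EAQ201 weights 63/37: 0.63 × 0.10 + 0.37 × 0.40 = 0.211.

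Either is the full 3.9-point effect. In general, the weight shift needed is 0.039 / spread, where spread is the difference in WOC share between the two groups:

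| Spread (points) | 10 | 20 | 30 | 40 | 50 |
|---|---|---|---|---|---|
| Weight shift needed (points) | 39 | 19.5 | 13 | 9.8 | 7.8 |

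**4. Power with a sampled, matched comparator.** Unstratified two-sample formula, n1 = 1000 EAQ201 women and n2 TMIST women:

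Power = Φ[(d − 1.96 × SE0) / SE1], with SE0 = √[p̄(1 − p̄)(1/n1 + 1/n2)] and SE1 = √[p1(1 − p1)/n1 + p2(1 − p2)/n2].

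For n2 = 1000 and 21.1% vs 25%, SE0 = 0.01883 and SE1 = 0.01881, so power = Φ[(0.039 − 0.0369)/0.01881] = 54%.

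| TMIST comparators | 21.1% vs 25% | 28.9% vs 25% |
|---|---|---|
| 1000 | 54% | 50% |
| 2000 | 66% | 63% |
| 5000 | 76% | 73% |

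With 1000 comparators, the difference detectable with 80% power is about 5.3 points downward or 5.7 points upward.

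**The case against.** The strongest reply is that the groups are closer than the concern suggests. EAQ201 women were eligible for TMIST and were approached by the same TMIST staff, usually at the same contact (Section 5). All NCORP sites and three others are invited, and Section 5 clears US sites that are actively enrolling to TMIST. EAQ201 sites are thus a subset of TMIST sites, and how far their enrollment mix differs is unknown. With only a 10-point spread between site groups, the weights would have to move by 39 points to create the full effect. Section 7.4 also models participation status on a TMIST sample aligned by site and time, and could yield a WOC contrast.

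Most of this stands as a limit on size. It does not remove the gap. Section 7.4 is exploratory and does not name WOC status as a covariate, and a shift well below 3.9 points already inflates the error rate.

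Three stronger readings are tempting but unsupported:
- A reader might infer that the dates are also unaligned. Section 5 already sets the same time period; 7.3 only fails to repeat it.
- A reader might infer that the comparator is every woman ever enrolled in TMIST. Section 7.3 is silent on this, and the source of its 25% is not given. The US-site table in 7.6 (September 2020) yields 228 + 30 = 258 per 1000 if Hispanic White women are counted as WOC, so the figure may already be a recent US one.
- A reader might infer that the English-only rule removes WOC from the decliner side alone. TMIST's language rule is not in these documents, so this cannot be judged.

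**Conclusion.** The point holds as a gap in the analysis specification. As written, 7.3 cannot distinguish a difference in participation from a difference in site mix, and the error can go either way, including toward the stated hypothesis. A 2-point shift from site mix gives about 29-30% rejection with no within-site difference, roughly six times the nominal 5%; a 3.9-point shift gives 79-81%.

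These figures rest on N = 1000, a fixed reference of 25%, and assumed shifts. The documents give no WOC share by site, so they do not support a claim that the result is biased by any particular amount. The consequence is confined to one secondary objective of an observational study; the primary comparison within EAQ201 is not touched by this point.

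**What to change.** In Section 7.3:

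1. Define the comparator as TMIST participants enrolled at EAQ201-activated sites during each site's EAQ201 accrual period.
2. Replace the one-sample test with a site-stratified two-sample analysis, either Cochran-Mantel-Haenszel or logistic regression with site. Restricting the sites is not enough by itself, because without a per-site cap the decliner and participant weights can still differ among the sites that remain.
3. Use all eligible TMIST women at those sites, not a 1:1 sample, to limit the loss of precision.
4. Restate the power for the comparator size expected.
5. State that the result applies to decliners able to complete questionnaires in English.

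No new data are needed: Table 1 lists race/ethnicity among the items collected from TMIST women, and 7.4 already plans selection by site and time. The cost is an SAP amendment and a lower stated power, which is not a slight change. By the unstratified formula, a 3.9-point difference has about 50-54% power with 1000 comparators and 73-76% with 5000. The present 80% depends on treating the TMIST share as known without error.

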### 7.4 Assess the effects of sociodemographic characteristics, and federal-, state- or local-level COVID-19 factors on TMIST participation, in WOC vs non-WOC.

For the exploratory objective ([7.1.3.5](#)), we will compare the effects of sociodemographic characteristics, federal-, state- or local-level factors (e.g. maximum number of COVID-19 cases, state unemployment during shelter-in-place, local unemployment during shelter-in-place) on TMIST participation, stratified by WOC vs non-WOC. We will fit a logistic regression model with TMIST participation status (EAQ201 participant or TMIST participant) as the response variable to investigate other sociodemographic (e.g., marital status, neighborhood SES, insurance type), federal-, state- or local-level factors (see **Table 2**). Regression modeling will be conducted with and without stratification by WOC vs non-WOC.

The analysis set will include the 1000 EAQ201 participants from this study and a corresponding number of TMIST participants, who will be randomly selected from the enrolled participants in the main TMIST study. The selection will be stratified by site and enrollment time. Assuming that the proportion of overall EAQ201 participants is from 0.20 to 0.50, **Table 5** below shows the power analysis of testing for the odds ratio in the logistic regression. The variables of interest can be continuous or categorical (binary). For instance, 2000 women (1000 EAQ201 participants versus 1000 randomly selected TMIST participants) achieves 90% power at a 0.050 significance level to detect a change in the proportion of EAQ201 participants from 0.50 at the mean of the testing variable to 0.538 when the value of the variable is increased to one standard deviation above the mean. This change corresponds to an odds ratio of 1.165. An adjustment was made since a multiple regression of the independent variable of interest on other independent variables in the logistic regression obtained an R-Squared of 0.10.

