We will also compare the sociodemographic characteristics of women who complete the EAQ201 participant survey with women who agree to participate in TMIST over the same time period using only data collected as part of the TMIST study that have also been collected as part of the current study. No additional data will be collected from women who participate in the TMIST study.

No additional participant-level data will be collected from TMIST participants related to COVID-19 given the supplement scope. We elected to more completely understand the effects of COVID-19 on those who declined participation in TMIST.

Site characteristics and recruitment process: All sites will receive \$30 per-case reimbursement for each eligible participant who registered to EAQ201. As with EAQ162CD, the study will provide some resources to assist the site, in particular: 1) site RA guides for engaging women who decline TMIST to enhance EAQ201 participation; 2) biweekly webinars/ phone calls for sites to check-in and discuss issues regarding recruitment and/or other study related issues, as needed. Sites that have implemented successful recruitment processes will be encouraged to attend and share their experiences.

Site Recruitment Plan: EAQ201 Study Chair or her designee will present the EAQ201 study to TMIST participating sites via standing TMIST Open Sites calls and through

direct email outreach to site TMIST PIs and lead TMIST research coordinators. This introduction to the study is expected to occur as close as possible to EA activation of the trial. The purpose of the study, site responsibilities, survey team responsibilities, and timeline will be presented on these calls. Along with materials to help support recruitment effort including phone script, study talking points, FAQs to help sites understand the study and to be able to communicate it to potential participants.

All EA1151 participating sites in the United States that are approved to enroll to EA1151 according to CTSU and actively recruiting and enrolling new participants to EA1151 based on at least one new enrollment attributed to the site in the most recent CTSU monthly enrollment report will be cleared to activate EAQ201 by ECOG-ACRIN upon obtaining EAQ201 NCI CIRB approval.

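### Section 7.4 limits the TMIST comparison group to a random draw without a stated reason; using all concurrent TMIST women could improve precision at little cost.

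*Combined protocol and SAP*

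**What the plan says.** Section 7.4 models TMIST participation by logistic regression, overall and separately in WOC and non-WOC. The analysis set is the 1,000 EAQ201 women (decliners) plus "a corresponding number of TMIST participants, who will be randomly selected from the enrolled participants in the main TMIST study". The next sentence stratifies the draw by site and enrolment time, without giving sampling fractions.

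The worked example reads "2000 women (1000 EAQ201 participants versus 1000 randomly selected TMIST participants) achieves 90% power at a 0.050 significance level", and for a continuous covariate "This change corresponds to an odds ratio of 1.165". The paragraph also begins its power statement with "Assuming that the proportion of overall EAQ201 participants is from 0.20 to 0.50", and Table 5 has rows with 50%, 40% and 20% EAQ201 women.

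Section 5 describes the comparator as women who join TMIST over the same period, without mentioning a subsample. It restricts the comparison to variables that both studies collect, and adds: "No additional data will be collected from women who participate in the TMIST study". Table 1 lists race/ethnicity, age, insurance and ZIP for the TMIST women.

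**The concern.** Controls are usually sampled because each one costs something to measure. Here the individual-level comparator data already exist, so an additional TMIST woman costs only a line in the extract. The decliners are the scarce group, and each additional eligible comparator adds information until the decliners alone limit precision.

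Stratifying by site and date is a reason to restrict who is eligible as a comparator. It is not a reason to stop at 1,000 if more eligible women exist. At stake is the width of the intervals around the participation odds ratios. This matters most in the WOC-stratified fit, where the plan's figures imply 100 to 250 decliners.

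**Working it through.** **Inputs.** 1,000 decliners; 90% power; alpha 0.05; R-squared 0.10 (Section 7.4). Section 7.4 does not state sidedness; a two-sided Wald test reproduces Table 5. WOC share among decliners: 10 to 25% planned, 16% from DCP-001 (Section 7.2). WOC share among TMIST participants: about 25% (Section 7.3). The number of concurrent TMIST women is not given, so it is varied as an assumption.

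**Formula.** For a continuous covariate, per standard deviation:

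OR = exp[(1.960 + 1.2816) / sqrt(I × (1 − R²))], with I = N·P·(1 − P) = n1·n0/(n1 + n0), where n1 is decliners and n0 is TMIST women.

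**Plan's figure.** I = 1,000 × 1,000 / 2,000 = 500. OR = exp(3.2415 / sqrt(450)) = exp(0.1528) = 1.165, as stated. All six continuous rows of Table 5 reproduce (power 0.899 to 0.902), and all six binary rows reproduce with N within 0.4%.

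**More TMIST women, decliners fixed at 1,000.** The standard error relative to 1:1 is sqrt((1 + 1/k)/2) for k TMIST women per decliner.

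| Ratio | I | Detectable OR | SE reduction |
|---|---|---|---|
| 1:1 | 500 | 1.165 | 0 |
| 1:1.5 | 600 | 1.150 | 9% |
| 1:2 | 667 | 1.141 | 13% |
| 1:4 | 800 | 1.128 | 21% |
| limit | 1,000 | 1.114 | 29% |

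Under 1:1, power at OR 1.128 is Φ(sqrt(450) × ln 1.128 − 1.960) = Φ(0.595), about 72%.

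**WOC stratum.** With 1,000 TMIST women there are about 250 WOC comparators; with 2,000, about 500; with 4,000, about 1,000. For 160 decliners, I goes from 160 × 250 / 410 = 97.6 to 160 × 1,000 / 1,160 = 137.9.

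| WOC decliners | OR, 250 comparators | OR, 1,000 comparators | SE reduction at 500 | SE reduction at 1,000 | Largest possible |
|---|---|---|---|---|---|
| 100 | 1.50 | 1.43 | 7% | 11% | 15% |
| 160 | 1.41 | 1.34 | 10% | 16% | 22% |
| 250 | 1.36 | 1.27 | 13% | 21% | 29% |

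**Table 5 set against the plan.** Every 40% or 20% row also raises the EAQ201 number, to between 1,200 and 2,100. No row pairs 1,000 decliners with more than 1,000 TMIST women, so the table does not show what a larger comparator would do for this study.

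**Where the formula does not carry over.** It treats women as independent. State- and local-level factors are shared by women in the same area, so more women from the same sites add less than shown. Section 7.4 names marital status as a covariate, but Table 1 lists it only for EAQ201 women; more TMIST women add nothing there. Neighborhood measures are tied to ZIP+4 for EAQ201 women, while the TMIST row says only ZIP, so ZIP-based gains hold only at the geographic detail that both groups share.

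**The case against.** The strongest reply is that the loss depends on a pool size that the documents never give. Valid comparators come from the same sites and period, and Section 5 expects EAQ201 enrolment to finish within a few months. Section 7.2 says TMIST accrual will continue for 4.4 years but states no rate. If about 1,000 concurrent women exist, nothing is lost. This stands. Planning a random draw suggests that a larger pool was expected, but not how much larger. A reader might take the 20% rows of Table 5 as evidence of four TMIST women per decliner; they are power scenarios, not pool estimates.

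A reader might also infer that the plan fixes 1:1 and discards data for no purpose. The text does not go that far. The number is loosely worded, the 1,000 against 1,000 case is given as an example, and the 0.20 to 0.50 range leaves ratios up to 1:4 open. The stratified draw has a purpose, alignment on site and calendar time. What remains is that no reason is given for limiting the number and that the statements need reconciling.

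Third, the objective is exploratory and has 90% power for an odds ratio of 1.165. In the WOC stratum the decliners are the limiting group, so even unlimited comparators reduce the standard error by only 15 to 29%. This also stands, and it limits the priority.

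Finally, if all concurrent women are used, the ratio of decliners to participants at each site partly reflects how actively that site recruited to EAQ201. That is a fair caution. Forcing the ratio is no remedy, however: a draw proportional to decliners within site and time would fix the decliner share at each site by design and hinder estimation of the state- and local-level effects that the objective seeks.

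**Conclusion.** The point holds as a conditional loss of precision. If the concurrent TMIST pool at EAQ201 sites exceeds 1,000, limiting the comparator to 1,000 makes standard errors larger than necessary for covariates held on both groups: race/ethnicity, age, insurance and ZIP-based measures. With independent observations, the avoidable part of the standard error is 9% at a pool of 1,500, 13% at 2,000 and 21% at 4,000, with a ceiling of 29%. In the WOC stratum it is 11 to 21% at a pool of 4,000, assuming that about 25% of TMIST women are WOC.

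Two stronger readings should be avoided. The documents do not support saying that every participation odds ratio loses precision, because marital status is not listed for TMIST women and area-level factors gain less than the formula suggests. Nor do they show the pooled analysis to be underpowered for its stated effect, since the plan's figure reproduces. This is a low-to-moderate priority improvement to an exploratory analysis.

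**What to change.** - Define the comparator in Section 7.4 as all TMIST women enrolled at EAQ201 sites while EAQ201 was open at that site, in line with Section 5.
- Use site and enrolment window to decide inclusion, not to force equal ratios.
- State how site clustering is handled in a way that still allows state-level factors to be estimated, for example a site random effect or cluster-robust standard errors.
- Restate Table 5 with 1,000 EAQ201 women against the TMIST number expected to be available, and remove the ambiguity between the corresponding-number wording and the 0.20 to 0.50 range.
- Limit the covariate list to variables held on both groups.
- If a random draw is kept, give the ratio, the sampling fractions and the reason.

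The cost is SAP wording and a larger data extract. No new data, participants or site work are needed.
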